Every admitted patient will be included for evaluation of the primary and secondary outcomes (a-e + j-k) regardless of the patient's cognitive status. However, the remaining secondary outcomes (f-i) will require that the patient is able to understand the Danish language and cognitively able to answer the questions meaningfully. A dedicated project nurse will assist during the hospital admission if required. A patient can be included several times due to recurrent dislocations which will be accounted for during statistical analysis.

Outcome/variable time table

Pre-admission (recall past 14 days)	Hospital ad- mission (Day 0)	Day 1	Day 3	Day 7	Day 14	Day 30	Day 90	Day 180	Day 365
Patient-reported outcomes									
NRS	NRS	NRS	NRS	NRS	NRS	NRS			
HOOS					HOOS		HOOS	HOOS	HOOS
EQ-5D					EQ-5D		EQ-5D	EQ-5D	EQ-5D
	Satisfaction								
Registry/Patient file outcomes									
	Time to reduction								
	Time to discharge								
	Per-operative Complications								
	Post-operative complications								
						Re- admissions			
						Mortality	Mortality		
Patient variables									
	Age								
	Sex								
	ASA-score								
	BMI								
	Specific comorbidities								
Prosthesis variables									
	Primary operation date								
	No. of previous dislocations								
	Type of prosthesis (incl. liner type)								

Information acquired from patient files: Information regarding patient-related factors (age, sex, ASA-score, BMI, and specific comorbidities) and prosthesis-related factors (primary operation date, number of previous dislocations, and type of prosthesis), as well as information regarding

30-days readmission and mortality, and 90-days mortality will be acquired from the patient files after acquired patient consent. The patient- and prosthesis-related factors will be used to control for potential confounding. The acquired patient file information is dated from admission to 90 days post-admission. The prosthesis-related information is dated to the primary operation date. We will only access patient files from patients who accept to participate, therefore 120 patients.

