As the acute treatment has been performed when the patient is asked for consent, we apply for the use of the data acquired during the acute treatment of the patient, regardless of whether they choose to participate in the secondary part of the study regarding the patient-reported outcomes, in order to not prolong the study unnecessary. This includes the patient- and prosthesis-related factors, as this will be used to control for potential residual confounding.

Sample size

Study sample size are based on the primary outcome “Time from arrival at the emergency entrance to prosthesis reduction”, applying a formula for RCT studies with clinically superiority design (21). The null-hypothesis dictates no difference in time from arrival at the emergency entrance to prosthesis reduction for patients following the Standard Pathway or the Fast-Track Pathway.

$$N = 2 \times \left(\frac{z_{1-\alpha} + z_{1-\beta}}{\delta - \delta_0} \right)^2 \times s^2$$

N = no. of patients in each group

Alpha-value = 0,05 (5% risk of type-1 error)

Beta-value = 0,90 (10% risk of type-2 error)

Delta-value (estimated true value between the two groups) \approx 4 hours

Delta₀-value (estimated clinical acceptable difference between the two groups) \approx 3 hours

S-value (pooled standard deviation (SD) for both groups) \approx 2.5 hours

A review of 16 randomly selected patients that was admitted to the University of Southern Denmark, Esbjerg, with a dislocated THA from January 2018 to May 2022 revealed a mean time from arrival at the emergency entrance to prosthesis reduction at 6 hours (range 2.7 – 9.0 hours) with a standard deviation at 1.6 hours.

$$N = 2 \times \left(\frac{1,645 \times 1,28}{4 - 3} \right)^2 \times 2,5^2 \approx 53 \text{ patients in each group}$$

Based on a review of the surgical procedures performed during the period 01.02 – 31.08.2022, we expect to admit 5-6 patients per month with a dislocated THA or HA, and we expect an attendance rate of >90% based on the primary outcome. Therefore, we will include 53 patients + 15% ≈ 60 patients in each group, due to the risk that specific comorbidities will lead to exclusion from the Fast-Track pathway by the anesthetic staff. It is thus expected that a total of 120 patients will be adhered to one of the two treatment algorithms over the course of 24 months.

Blinding

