This study concerns emergency research without the possibility of informed consent prior to intervention, and the patients will not be informed regarding their participation in a scientific study on arrival. Post-reduction, the patients are encouraged to participate in the second part of the study involving patient-reported outcome measures. The patient will not be informed of whether they have been adhered to the standard or Fast-track treatment strategy and are therefore blinded regard the treatment.

The orthopedic and anesthetic staff are not informed regarding the initiation of the current study and are therefore blinded in terms of the aim. The staff will be thoroughly instructed to adhere to the Fast-track strategy at the time for pathway shift.

Patient information

After reduction of the prosthesis, the patients are admitted to the ward at the Dept. of EM, regardless of the treatment received. During the admission, the patient will be interviewed by a dedicated study-nurse and informed about the study, without revealing the allocated treatment pathway. The rooms are single-patient only, in order to secure that the information can be given undisturbed. The patients will be screened for eligibility (cognitive status, language) for participation in the secondary part of the study, and the nurse will deliver patient information including a study overview depicting the timepoints for evaluation. When recruiting the patient for the secondary part of the project, it is stated that this is a scientific trial and that the patient has the right to have a companion present during the information. The patients are encouraged to respond before discharge, typically 12-24 hours after arrival.

Up to 15-20% of patients admitted to the hospital with a dislocated THA/HA is cognitively impaired due to dementia in a degree that hinders reasonable questionnaire response. These patients require the same acute treatment as any other patient, and there is no reason for not including them in this study. Information will be given to the patient's relatives, and we will ask for their permission to include the already obtained journal data in the study.

Patent information folder is found in the appendix (in Danish).

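### 30-day readmission and 30- and 90-day mortality are promised for every admitted patient, but the files they come from are opened only for patients who consent

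*Protocol*

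**What the plan says.** The Outcomes section lists 30-day readmission as outcome d and 30- and 90-day mortality as outcome e. It then sets the population: "Every admitted patient will be included for evaluation of the primary and secondary outcomes (a-e + j-k"), regardless of cognitive status. Only f–i, the patient-reported outcomes, are limited to patients who understand Danish and can answer meaningfully.

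The paragraph on information acquired from patient files, in the same section, sets a different condition for d and e: "30-days readmission and mortality, and 90-days mortality will be acquired from the patient files after acquired patient consent". The same sentence puts the patient factors (age, sex, ASA score, BMI, comorbidities) and the prosthesis factors under consent. The paragraph ends: "We will only access patient files from patients who accept to participate, therefore 120 patients".

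The next paragraph, just before Sample size, makes an exception: "we apply for the use of the data acquired during the acute treatment of the patient, regardless of whether they choose to participate" in the part on patient-reported outcomes. Its scope is then extended: "This includes the patient- and prosthesis-related factors, as this will be used to control for potential residual confounding".

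For patients with dementia, the Patient information section says that relatives will be informed and asked for permission to use journal data already obtained.

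The Sample size section says where 120 comes from: "a total of 120 patients will be adhered to one of the two treatment algorithms over the course of 24 months". The Ethics section reports that the ethics committee's permission is not required and that the study has local approval as a treatment-quality study. It does not say what that approval allows for patient files.

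**The concern.** Two instructions in one section cannot both be followed once any patient refuses, dies before being asked, or cannot consent. One asks for d and e on everybody; the other allows them only for those who accept.

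This matters because the stated purpose is to shorten time to reduction and hospital stay without changing complications, readmission or mortality. Outcomes d and e carry that condition. Consent is sought after reduction, during the admission, so mortality restricted to consenters is conditional on surviving long enough to be asked. The two pathways run in successive years, so any difference between years in who is asked or who accepts would enter the comparison.

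This is not a detail to leave to an analysis plan. Whose records may be opened, and on what basis, is a protocol rule, and an analysis cannot recover data that were never collected.

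**Working it through.** **Step 1. Set the rules side by side, by data item.**

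| Data item | Population promised | Rule in the patient-file paragraph | Reached by the exception paragraph? |
|---|---|---|---|
| Time to reduction, a–c | Every admitted patient | Not named in the consent sentence; files opened for acceptors only | Yes, on a natural reading: they arise during the admission |
| d, 30-day readmission | Every admitted patient | After consent; acceptors only | No: not named, and not acute-treatment data |
| e, 30- and 90-day mortality | Every admitted patient | After consent; acceptors only | No: not named (a death during the acute stay might count; the text does not say) |
| Patient and prosthesis factors | To be used for confounding control | After consent; acceptors only | Yes, expressly |
| f–i | Patients able to answer | Consent to the second part | Not needed; no conflict |

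The contradiction is in the d and e rows. The row for the factors is a lesser misalignment: the only-acceptors sentence bars what the next paragraph permits.

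**Step 2. Check whether the relatives' route closes the gap.** It covers journal data already obtained when relatives are asked. Readmissions up to day 30 and deaths up to day 90 lie mostly after that, and the text does not mention them.

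**Step 3. Trace the figure of 120.** Inputs are from Sample size, with 53 per group taken as printed.

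- 53 × 1.15 = 60.95, given in the protocol as about 60 per group.
- 2 × 60 = 120.
- Accrual: 5 per month × 24 months = 120; 6 per month × 24 = 144.

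So 120 is the number expected to follow one of the two pathways, and these patients are included without prior consent. With N patients included and a proportion p accepting, the acceptors number N × p. Setting 120 × p = 120 gives p = 1. The patient-file paragraph therefore equates acceptors with treated patients, which holds only if all of them accept.

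**Step 4. Look for a consent rate.** There is none. The attendance rate above 90% is stated for the primary outcome, so it does not tell us how many will agree to file access.

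**The case against.** The strongest defence is that the protocol has a recognisable two-part design. All patients are included without prior consent, a–e and j–k are for everyone, and consent concerns the patient-reported part. The exception paragraph follows directly on the only-acceptors sentence and reads as a specific carve-out from it. That stands for time to reduction and for the confounders, where the intent is clear and only the wording needs aligning. It does not stand for d and e, which the carve-out does not mention and which the preceding paragraph names as needing consent.

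A reader might infer several stronger things that the protocol does not support.

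- *That the primary outcome is at risk.* The time table lists time to reduction under "Registry/Patient file outcomes". But that heading does not make the patient file the only source, the consent sentence does not list time to reduction, and it is acute-treatment data covered by the exception.
- *That consent is the only route to any record.* The Patient information section says what consent permits, including access for control and monitoring. It does not say that nothing else permits access.
- *That 18 to 24 of the 120 are lost through dementia* (0.15 × 120 = 18; 0.20 × 120 = 24). The source sentence is "Up to 15-20% of patients admitted to the hospital with a dislocated THA/HA is cognitively impaired due to dementia", to a degree that hinders answering questionnaires. That is an upper figure, refers to all admissions before exclusions, and concerns questionnaires rather than consent. Relatives may also be asked.
- *That a particular acceptance rate is needed or a particular number will refuse.* No refusal rate is given. Dividing 120 by 144 admissions gives 83%, but this uses the upper accrual figure and ignores exclusions, so it is only a best case. A patient may also be included more than once, so 120 may count episodes rather than people to be asked.

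Finally, limiting file access to acceptors may be deliberate protection of privacy. The terms of the local approval and the patient information folder are not shown, so that limit cannot be called wrong in itself.

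**Conclusion.** The point holds as an internal contradiction on outcomes d and e. They are promised for every admitted patient and made obtainable only for consenters, and neither the exception paragraph nor the relatives' route reconciles the two. Two smaller points hold with it: the only-acceptors sentence is out of line with the exception for the confounders, and 120 is wrongly presented as the number who accept.

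The number of patients missing from d and e is unknown, and so are the size and direction of any bias between the two years. The conclusion rests on reading the text literally, and on the assumption that at least one included patient refuses, dies before being asked, or cannot consent to follow-up. These are secondary outcomes and the sample size does not rest on them. The point should be fixed because readmission and mortality carry the safety condition in the aims. It does not undermine the primary comparison.

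**What to change.** Rewrite the population statement in Outcomes, the two patient-file paragraphs and the paragraph on relatives in Patient information so that they give one access rule per data item. Tie that rule to the local treatment-quality approval reported under Ethics.

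- If that approval allows it, collect d and e for all included patients in both years and limit consent to f–i. Say expressly that this covers those who decline the second part, patients with dementia, and patients who die before being asked.
- If it does not, state that d and e apply to consenters only, limit the conclusion on readmission and mortality to them, and report the number and reasons for missing d and e in each period.

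In either case, bring the only-acceptors sentence into line with the exception for the patient and prosthesis factors, and remove or correct the claim that acceptors number 120.

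The cost is wording, and possibly confirmation of the scope of the local approval. Treatment, visits and sample size do not change. Under the second option, d and e may be reported for fewer than 120 patients.

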The dislocated prosthesis is usually managed by a simple, closed reduction maneuver under general anesthesia with or without muscle relaxation, resulting in open surgical reduction rarely being needed (9-11). Time from admission to actual reduction often includes various steps (incl. several patient transfers between emergency units, radiology departments, operating theaters) which causes an unnecessarily long period of pain for the patient. In 2015, a fast-track system was introduced at Hvidovre Hospital on a trial basis for patients highly suspected for THA/HA dislocation (12). This resulted in a significant decrease in the time from arrival to reduction and overall time of hospitalization, without resulting in more complications. The study was retrospective and did not measure how patients experienced the change in practice.

A fast-track system must be specially designed for the local departments, due to differences in the logistical options from hospital to hospital. The purpose of this study is to design a fast-track pathway for patients referred to the University Hospital of Southern Denmark, Esbjerg, with high probability of having a dislocated hip prosthesis with the primary aim to reduce the time from arrival to reduction and the total hospitalization time. Secondary aims are to

- investigate whether quicker prosthesis reduction influences on hip function and quality of life afterwards
- reduce the pain experience immediately and in the long term
- increase patient satisfaction

without changing the overall complication rate and readmission/mortality

Methods:

Trial design

The study is designed as a prospective observational cohort trial, adhering to the STROBE guidelines (13). The present protocol will be registered at clinicaltrials.org and submitted for publication in an international journal.

Setting

The study is conducted at the University Hospital of Southern Denmark, Esbjerg, as a collaboration between the Department of Orthopedics, Department of Anesthesiology, Department of Radiology, and Department of Emergency.

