The patients are informed that consent gives the trial manager, sponsor and sponsor's representatives as well as any supervisory authority direct access to obtain information in the patient's medical record, etc., including electronic medical records, in order to see information about the subject's health, which is necessary as part of the implementation of the research project and for control purposes, including self-control, quality control and monitoring, which they are obliged to carry out.

Statistics

Mean values with standard deviation (SD) are given for normally distributed data, while median values with interquartile range (IQR) are given for skewed data. In case of normally distributed data, two-sample t-test is used. Mann-Whitney U-test is used to compare continuous nonparametric variables and chi-square test is used to compare categorical variables. STATA version 18 will be used for all statistical analyses.

Economy

The main investigator and initiator is [name], Ph.D., post.doc.

The study is conducted as a collaboration between the Department of Orthopedics, Department of Anesthesiology, Department of Radiology, and Department of Emergency Medicine, University Hospital of Southern Denmark, Esbjerg. There are no special economics involved in the study between the departments, as the study is carried out as a part of normal daily, acute activity.

Vestjysk Orthopedic Fund will be applied for covering expenses to hardware (computer, Ipad etc.)

The Region of Southern Denmark's Research Fund will be applied for covering salary to a dedicated study nurse.

Grants are administered via an account that is subject to public audit.

There are no conflicts of interest.

Ethics

Permission to store and handle data is obtained upon application to the Region of Southern Denmark's internal register (24/34681). The Danish Law of data protection is observed.

The regional ethics committee has been applied for permission to conduct the study under special circumstances as acute research without the possibility of obtaining informed consent from the

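### The sample size is built on a 3-hour superiority margin, but the stated null is no difference and the named tests carry no margin

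*Protocol*

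**What the plan says.** All the sizing is in the protocol's Sample size section. It describes the method as "applying a formula for RCT studies with clinically superiority design". It sets the assumed true difference at about 4 h and a second quantity, delta0, at about 3 h, described as the "estimated clinical acceptable difference between the two groups". The pooled SD is 2.5 h, the type I error is 5% with z = 1.645 (one-sided), and the type II error is 10%. The divisor is 4 − 3 = 1 h. The result is 53 per group, raised by 15% to about 60.

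The same paragraph gives the hypothesis: "The null-hypothesis dictates no difference in time from arrival at the emergency entrance to prosthesis reduction" for patients on the two pathways.

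The Statistics section gives the analysis: "In case of normally distributed data, two-sample t-test is used", with a Mann-Whitney test for continuous data that are not normal. It mentions no margin, shifted null, sidedness or confidence-limit rule.

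The aim, at the end of the Background section, is a pathway "with the primary aim to reduce the time from arrival to reduction and the total hospitalization time". The 3 h figure appears nowhere outside the sizing.

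**The concern.** Subtracting delta0 = 3 h in the divisor powers the trial to show a gain of more than 3 h, that is, to reject H0: mean(standard) − mean(fast-track) ≤ 3 h. The stated null is a difference of zero. These are different hypotheses for the same primary outcome, and they appear in one paragraph. The null, the named tests and the aim agree with one another; delta0 is the piece that does not fit.

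The matter at stake is what a positive result means. A significant result from the named tests shows that fast-track is faster. It does not show that it is faster by more than 3 h. A reader told that the trial was a clinical-superiority design with a 3 h figure and 90% power could take it to show the latter. If the hypothesis is left open until the data are in, the result could also decide which one is claimed.

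**Working it through.** **Inputs (protocol, Sample size).** Assumed gain δ = 4 h; δ0 = 3 h; SD s = 2.5 h; z = 1.645 and 1.28; n = 53 before and 60 after the allowance. The local review of 16 patients gave SD 1.6 h, used below as a sensitivity value. The protocol does not give the sidedness of the named tests; I take the zero-null test as two-sided 5% and the margin test as one-sided 5%, as in the formula. Calculations are for the t-test with independent, unadjusted observations.

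**1. The plan's own figure.** The printed formula is N = 2 × [(z₁₋α + z₁₋β)/(δ − δ0)]² × s².
- With the z-values summed, as the formula has it: 2 × 2.925² × 6.25 = 106.9, so 107 per group.
- With the z-values multiplied, as the substitution prints: 2 × (1.645 × 1.28)² × 6.25 = 55.4.
- Summed but without the factor 2: 2.925² × 6.25 = 53.5, the closest match to 53.

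So 53 does not follow from the formula. That is a separate arithmetic fault. Correcting it to 107 would leave the present problem in place, because 107 is still sized for a 3 h margin.

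**2. Size under the stated null (δ0 = 0).**
- One-sided: 2 × (2.925/4)² × 6.25 = 6.7, so 7 per group.
- Two-sided: 2 × ((1.96 + 1.28)/4)² × 6.25 = 8.2, so 9 per group.
- Using the t distribution, 8 and 10.

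**3. Observed gain needed for significance.** SE = s × √(2/n). The thresholds are t × SE against zero and 3 + t × SE against the margin.

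| SD | n per group | SE (h) | Against zero, two-sided 5% | Against 3 h, one-sided 5% |
|---|---|---|---|---|
| 2.5 h | 53 | 0.486 | 0.96 h | 3.81 h |
| 2.5 h | 60 | 0.456 | 0.90 h | 3.76 h |
| 1.6 h | 53 | 0.311 | 0.62 h | 3.52 h |
| 1.6 h | 60 | 0.292 | 0.58 h | 3.48 h |

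If the zero-null test is also one-sided, its thresholds at SD 2.5 h are about 0.81 h and 0.76 h. At SD 2.5 h, an observed gain between about 1 h and 3.7 h passes the zero-null test and fails the margin test.

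**4. Power at a true 4 h gain (non-central t).**

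| SD | n per group | Against 3 h, one-sided 5% |
|---|---|---|
| 2.5 h | 53 | 66% |
| 2.5 h | 60 | 70% |
| 1.6 h | 53 | 94% |
| 1.6 h | 60 | 96% |

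Normal-approximation check at SD 2.5 h: 1/0.486 − 1.645 gives 0.661, and 1/0.456 − 1.645 gives 0.707. Against zero, power exceeds 99% at either size with SD 2.5 h.

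**5. Gain detectable with 90% power against zero (two-sided, SD 2.5 h).** 1.59 h at 53 per group and 1.49 h at 60.

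**The case against.** The strongest reply is that little is lost. The zero-null test keeps its type I error, has more than ample power for the assumed gain, and answers the stated aim. No section says that superiority beyond 3 h will be claimed. This stands, and it is why the remedy is mainly a correction of the text.

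A second reply is that the 66% to 70% power and the 107 per group come from the arithmetic fault, not from the mismatch. That is also right: with the sum done correctly, a consistent margin design would have 107 per group and 90% power. These figures therefore matter here only if the sponsor does want the 3 h margin at the planned size. The mismatch itself does not depend on them, since no version of the printed formula with delta0 = 3 h gives the power for a null of zero.

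A third reply is that a t-test can be run against 3 h, and that an analysis plan might say so. It can, but the protocol's own null rules that reading out, and the contradiction lies inside the Sample size section whatever an analysis plan adds.

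Finally, the protocol says that recurrent admissions will be accounted for and that patient and prosthesis factors will be used against confounding. The final primary comparison may thus be more than a plain two-sample test. This limits how exactly the figures above describe it, but does not restore a margin.

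**Conclusion.** The concern holds. The sizing belongs to H0: gain ≤ 3 h, while the stated null, the named tests and the aim all belong to a null of zero. The stated 53 per group with 90% power describes neither at the protocol's inputs: at SD 2.5 h, power at a true 4 h gain is above 99% against zero and 66% to 70% against 3 h.

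The two hypotheses differ by almost 3 h in the observed gain that counts as success, at either SD. The power shortfall against the margin, by contrast, depends on the SD and disappears at 1.6 h. The result rests on the t-test, independent observations and the sidedness stated above. The trial can still meet its stated aim; the power statement and the superiority description need correcting.

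**What to change.** Make the null, the sizing and the test agree before any analysis.

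**Preferred: keep the null of no difference.** Delete delta0 and the clinical-superiority wording. State the power against zero: above 99% at 60 per group for a true 4 h gain with SD 2.5 h, and 90% for a true gain of about 1.5 h. State the sidedness, and that these figures assume independent, unadjusted observations. Report the mean difference in time to reduction with its confidence interval (bootstrap if the data are skewed), so that readers can see how it compares with 3 h. The cost is wording and one restated power figure; data collection and recruitment do not change.

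**Only if superiority beyond 3 h is truly intended:** state H0: mean(standard) − mean(fast-track) ≤ 3 h, and require the lower limit of the two-sided 90% confidence interval for the mean difference (bootstrap if skewed) to exceed 3 h. Then either state the power as about 70% at 60 per group (66% at 53) for SD 2.5 h, or recruit about 107 per group, or 107 × 1.15 ≈ 123 with the protocol's allowance. The protocol says "we expect to admit 5-6 patients per month with a dislocated THA or HA". At that rate 107 takes 107/6 to 107/5, about 18 to 21 months per pathway, and 123 takes about 21 to 25, instead of the planned 12. This route is not a cheap change.

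### The sample-size formula with its own inputs gives 107 per group, not 53, and the 3-hour margin it uses is not the null hypothesis the protocol states

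*Protocol*

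**What the plan says.** The Sample size section of the protocol sizes the study on time from arrival to reduction, "applying a formula for RCT studies with clinically superiority design". The per-group formula is N = 2 × ((z for alpha + z for power) / (delta − delta0))² × s². The inputs are alpha 0.05, "Beta-value = 0,90 (10% risk of type-2 error"), delta 4 h, delta0 3 h and a pooled SD of 2.5 h. The worked line puts in 1.645 and 1.28 and reports 53 per group. It then says: "Therefore, we will include 53 patients + 15% ≈ 60 patients in each group", which makes 120 in total.

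The same section defines the hypothesis differently: "The null-hypothesis dictates no difference in time from arrival at the emergency entrance to prosthesis reduction" between the two pathways. It also reports a review of 16 patients with a dislocated THA, with a mean of 6 h, "with a standard deviation at 1.6 hours".

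On the analysis, the Statistics section says: "In case of normally distributed data, two-sample t-test is used". A Mann-Whitney test is named for non-normal continuous data. Neither is tied to a 3-hour margin.

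**The concern.** Two things do not fit together. First, the printed formula and inputs do not produce the printed answer, and the wrong answer is carried forward to 60 per group and 120 overall. Second, the formula is for showing a gain larger than 3 h, whereas the stated null and the named tests concern any difference at all.

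At stake is the meaning of the 90% power. If the aim is to show a gain beyond 3 h, the risk of missing a true 4 h gain is much higher than the stated 10%. If the aim is to show any gain, the calculation does not belong to that aim. The protocol also does not say what to conclude from a result that beats zero but not 3 h when the study was sized to beat 3 h.

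**Working it through.** **Inputs** (Protocol, Sample size): z = 1.645 (one-sided 5%) and 1.28 (90% power); delta 4 h; delta0 3 h, so delta − delta0 = 1 h; s = 2.5 h, so s² = 6.25; N is per group; pilot SD 1.6 h.

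**Step 1: try to reproduce 53.**

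- Formula as stated: 2 × (1.645 + 1.28)² × 6.25 = 2 × 8.556 × 6.25 = 106.9, so **107 per group** (108 with unrounded z values).
- Worked line read literally, with a multiplication sign between the z values: 2 × (1.645 × 1.28)² × 6.25 = 55.4. That sign may be a text-extraction fault, so nothing is built on it.
- Sum of z values, factor 2 omitted: 8.556 × 6.25 = 53.5. This matches the reported 53, although the factor 2 is printed in both the formula and the worked line.

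Neither reading of the printed line gives 53. The omitted factor 2 is the likely cause, but that is an inference; the mismatch itself is not. The inflation step is essentially sound: 53 × 1.15 = 60.95, reported as about 60.

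**Step 2: power against the 3-hour margin.** With n per group and one-sided 5%, power = Φ( 1 / (SD × √(2/n)) − 1.645 ).

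| SD | n = 53 | n = 60 |
|---|---|---|
| 2.5 h (stated) | 2.059 − 1.645 = 0.414 → 66% | 2.191 − 1.645 = 0.546 → 71% |
| 2.0 h | 2.574 − 1.645 = 0.929 → 82% | 2.739 − 1.645 = 1.094 → 86% |
| 1.6 h (pilot) | 94% | 96% |

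With 107 per group and SD 2.5 h the same expression returns 90%, which confirms the corrected N. A calculation with the noncentral t-distribution changes these figures by at most about half a percentage point. With two-sided 5%, power at SD 2.5 h falls to 54% at 53 and 59% at 60.

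**Step 3: what SD would make 53 or 60 right?** Solving for 90% power, SD = √(n/2) / 2.925. This is 5.148 / 2.925 = 1.76 h for 53 and 5.477 / 2.925 = 1.87 h for 60. At SD 1.6 h the formula needs 2 × 8.556 × 2.56 = 43.8, so 44 per group.

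**Step 4: the stated null (delta0 = 0).** At SD 2.5 h the same formula needs 2 × (2.925/4)² × 6.25 = 6.7, so 7 per group. With z = 1.96 in place of 1.645 it needs 2 × (3.24/4)² × 6.25 = 8.2, so 9. A two-sided 5% t-test with 53 per group has power above 99.9% for a true 4 h difference and 98% for 2 h (99% for 2 h with 60).

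**The case against.** The strongest reply is that the comparison the protocol actually describes is not short of patients. The primary aim is simply to reduce the time, the stated null is no difference, and the named tests have no margin. The 3-hour figure occurs only as a sample-size input, and no conclusion about exceeding 3 h is promised anywhere. On that reading a result that beats zero rejects the stated null, and enrolment need not change. This stands, and it limits the consequence: the study is not underpowered for the null it states. It does not rescue the calculation, because for that null the formula asks for about 7 to 9 per group, so the printed derivation does not justify 53.

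A second reply is that 2.5 h may be cautious. The only observed SD is 1.6 h. Assuming normality, 16 patients give a 95% interval of about 1.2 to 2.5 h (1.6 × √(15/27.49) to 1.6 × √(15/6.26)), so the planning value lies at its upper end. This also stands in part: the loss of power against the margin depends on the SD. But 2.5 h is the protocol's own choice. The pilot covers THA patients under current practice only, while the study also enrols HA patients and a new pathway. The break-even values of 1.76 to 1.87 h lie inside that interval, so the pilot does not settle the matter.

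Finally, the 71% assumes that all 60 per group are analysed. The extra 15% is there to cover exclusions, so 66% at 53 is closer to the planned evaluable number.

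**Conclusion.** The concern holds. The protocol's formula and inputs give 107 per group, twice the reported 53. For the 3-hour margin at SD 2.5 h and one-sided 5%, the type-2 error is 34% at 53 per group and 29% at 60, about three times the stated 10%. The shortfall rests on that SD: at 2.0 h power is 82–86%, and at the pilot 1.6 h it is 94–96%. Separately, the formula's margin contradicts the stated null of no difference and the named tests. For that null 53 to 60 per group is ample, but the 90% was not calculated for it. The stated sample size and power therefore need correction before the results are compared, whichever hypothesis is meant.

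**What to change.** Correct the worked line to the sum of the z values with the factor 2, and relabel beta as 0.10 (power 0.90). Then state one hypothesis for the primary outcome and make the null, the calculation and the test agree.

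- **If the 3-hour margin is meant:** write the null as a gain of at most 3 h, specify a test against that margin with its sidedness, and present 120 patients as the feasible number with power of about 66–71% at SD 2.5 h. Alternatively, justify a smaller SD explicitly. Do not print 107 beside 60 without this explanation.
- **If no difference is meant:** redo the calculation with delta0 = 0, give the power of that test at 53 to 60 per group, and drop the 3-hour margin from the sizing.

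Either route is a change of wording and needs no extra enrolment. Keeping the margin, SD 2.5 h and 90% power together would need 2 × 107 = 214 evaluable patients. The expected 5–6 admissions a month give only 120–144 over 24 months. The cost is a less favourable power statement or a justified SD in the first case, and giving up a margin-based claim in the second. The choice should be fixed before the two periods are compared, so that it cannot depend on the result.
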